## 7.5 Sample Size

The total sample size will be approximately 350 participants. We do not know in advance how many will opt to take or not take HCQ. The table below provides the detectable difference in positive SARS-CoV-2 rate for different proportions of participants in the treated and control groups. For example, if two-thirds of the sample opt to take HCQ, we will have 80% power to detect a difference in positive SARS-CoV-2 rate of approximately 15 percentage points (e.g., a 35% PCR positivity rate in the control group and a 20% PCR positivity rate in the HCQ group). These calculations assume a two-sided Type I error rate of 0.05. The exploratory endpoints remain independent of enrollment in Group A vs. Group B.

Treatment Group	Control Group	Detectable difference
175	175	0.14
230	120	0.15
260	90	0.17

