**Protocol Summary**

Title	Off label study to evaluate the efficacy of hydroxychloroquine as prophylaxis to prevent severe acute respiratory syndrome coronavirus 2 (SARS-CoV-2) infection among Health Care Workers (HCWs) who are at high risk of occupational exposure to SARS-CoV-2 Short Study Title: COVID-19 HCWP HCQ Study
Brief Summary	The HCW Prophylaxis (HCWP) Study, single, open and off label intervention study. Up to 350 participants will be assigned to group that takes HCQ or group that opts to not take study medication. Participants will be UNM HEALTH SYSTEM HCW at high risk for occupational exposure to SARS-CoV-2. Study timepoints will include Day 1 screening/enrollment, 30 day, 60 day, and 90 day assessments. Questionnaires will be collected in all timepoints.
Phase	Off label use of HCQ
Primary Objectives	To evaluate the efficacy of hydroxychloroquine (HCQ) for prophylaxis (HCWP) to prevent severe acute respiratory syndrome coronavirus 2 (SARS-CoV-2) infection among Health Care Workers High Risk of Occupational Exposure to SARS-CoV-2
Methodology	The Health Care Worker Prophylaxis (HCWP) Study, single, open and off label intervention study
Primary Endpoint	Number of HCW who test positive for SARS-CoV-2 while in the trial as determined by polymerase chain reaction assays from standard of care swaps.
Study Duration	12 months
Participant Duration	Participant Study period: up to 90 days for both groups, inclusive of those who elect to convert from Group B to Group A.
Duration of IP administration	Up to 90 days
Population	Total number of participants: Up to 350 UNM HEALTH SYSTEM health care workers with high risk of occupational exposure to SARS-CoV-2 Group A: up to 275 (HCW choose to be provided HCQ) Group B: up to 75 (HCW choose not to be provided HCQ)
Study Sites	UNM HEALTH SYSTEMS
Number of participants	Up to 350
Description of Study Agent/Procedure	Hydroxychloroquine- oral administration 
 
• Duration: up to 90 days or until meeting study termination criteria
 
• Loading dose: 600 mg once for the first day
 
• Maintenance dose: 200 mg, daily
 
 
Hydroxychloroquine is licensed for the chemoprophylaxis and treatment of malaria and as a disease modifying antirheumatic drug. It has a long history of being safe and well tolerated at typical doses. HCQ has antiviral activity in vitro against coronaviruses, and specifically Covid-19.

Key Procedures	Questionnaires

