#### Total number of participants: 350 (Group A and B)

- Group A: up to 275 (HCW who choose to be provided HCQ)
- Group B: up to 75 (HCW who choose not to be provided HCQ)

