### **5.2.3 Visit for Switching from Group B to Group A**

This study will allow participants to switch from Group B to Group A. If the previous visit is more than 7 days, survey collection will be done at the time of switch over. Switched participants will follow the study agent administration described in 4.7.1.2. Participants will be rescreened using screening form at the time of switch.

- Group A: approximately up to 275 (HCW choose to be provided HCQ)
- Group B: approximately up to 75 (HCW choose not to be provided HCQ)

Subjects who switch from Group B to Group A will not be replaced.

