### 7.4.2 Analysis of the Primary Efficacy Endpoint(s)

Detection of SARS-CoV-2 RNA by PCR will be the primary endpoint and will be compared between treatment groups (prophylaxis vs. no prophylaxis). Positive SARS-CoV-2 will be defined as a binomial variable (i.e., positive SARS-CoV-2 or no positive SARS-CoV-2) and analyzed using Wilcoxon rank analysis. Potential confounders of the primary endpoint will be addressed by using standard statistical matching techniques, such as propensity score matching, and logistical regression to assess for confounding by exposure risk, demographic factors and comorbidities that are known or suspected to affect the likelihood of developing SARS-CoV-2 infection.

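### Every row of the sample-size table has more controls than the Group B cap of 75; at 275/75, the only split that fills 350, the 35% vs 20% example has about 65% power by the method that fits the table (76% at best), not 80%.

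*Combined protocol and SAP*

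**What the plan says.** Section 7.5 plans about 350 participants and says that the split between takers and non-takers is not known in advance. It offers three splits (HCQ/control) with detectable differences: 175/175 (0.14), 230/120 (0.15) and 260/90 (0.17). The worked example is the middle row: "if two-thirds of the sample opt to take HCQ, we will have 80% power to detect a difference in positive SARS-CoV-2 rate". The difference is put at about 15 points, illustrated by positivity of 35% among controls against 20% among HCQ takers. On the method it says only this: "These calculations assume a two-sided Type I error rate of 0.05".

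The enrolment limits appear in three other places:

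- Protocol Summary, Population: "Group B: up to 75 (HCW choose not to be provided HCQ"), with Group A limited to 275.
- Section 4.2.1, total number of participants: "Group B: up to 75 (HCW who choose not to be provided HCQ"), again with 275 for Group A.
- Section 5.2.3: "Group B: approximately up to 75 (HCW choose not to be provided HCQ"), with Group A similarly qualified. The same section lets Group B members move to Group A without being replaced.

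Section 7.4.2 says that the primary endpoint will be "analyzed using Wilcoxon rank analysis".

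**The concern.** The control groups in the table exceed the Group B cap by 15, 45 and 100 people. Because 275 + 75 = 350, the two caps and the planned total leave one split, and that split is not in the table. Power in a two-group comparison depends mainly on the smaller group, so a table that stops at 90 controls is more optimistic than the design the caps describe.

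This is the only power statement in the plan. A reader who relies on it would take the risk of missing a fall from 35% to 20% to be 20%, when under the caps it is higher. A null result could then be given more weight than it deserves.

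**Working it through.** **Inputs.** From section 7.5: two-sided alpha 0.05, target power 80%, control rate 35%, HCQ rate 20%, total 350 and the three tabulated splits. From the Protocol Summary and section 4.2.1: caps of 275 and 75.

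**Step 1: reproduce the plan's figures.** No formula is named, so several standard ones were tried. The one that matches everything printed, using the document's own rates, is the two-proportion Z test with unpooled variance and continuity correction:

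power = Φ[(d − c)/SE − 1.96], where c = ½(1/n₁ + 1/n₂) and SE = √(p₁q₁/n₁ + p₂q₂/n₂).

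At 230/120 with 20% vs 35%:

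- c = ½(1/230 + 1/120) = 0.0063
- SE = √(0.16/230 + 0.2275/120) = 0.0509
- power = Φ(0.1437/0.0509 − 1.96) = Φ(0.862) = 80.6% (stated: 80%)

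Solving for the difference that gives 80% power, with the HCQ rate held at 20%, gives 0.137, 0.149 and 0.166. These round to the printed 0.14, 0.15 and 0.17. With the same HCQ rate, the alternatives miss the table: pooled gives 0.132/0.138/0.149, pooled with correction 0.138/0.145/0.157, and unpooled without correction 0.131/0.142/0.158.

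**Step 2: apply the same method to the split that the caps allow.** At 275/75:

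- c = ½(1/275 + 1/75) = 0.0085
- SE = √(0.16/275 + 0.2275/75) = 0.0601
- power = Φ(0.1415/0.0601 − 1.96) = Φ(0.394) = 65.3%

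| HCQ/control | Within caps? | Power, 35% vs 20% | Detectable difference at 80% power |
|---|---|---|---|
| 175/175 | no | 86.6% | 0.137 |
| 230/120 | no | 80.6% | 0.149 |
| 260/90 | no | 72.0% | 0.166 |
| 275/75 | yes | 65.3% | 0.179 |

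**Step 3: see how far the answer depends on the formula.** Power at 275/75 for 35% vs 20%:

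| Method (two-sided) | Power |
|---|---|
| Unpooled with correction (fits the table) | 65.3% |
| Unpooled | 70.4% |
| Pooled with correction | 71.3% |
| Fisher exact | 73.0% |
| Arcsine | 73.9% |
| Pooled | 75.9% |
| Wilcoxon, tie-corrected, exact enumeration | 76.0% |

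By the other normal-approximation tests, with HCQ at 20%, the detectable difference at 275/75 is 0.159 (pooled), 0.168 (pooled with correction) and 0.170 (unpooled).

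**Step 4: find how many controls the example needs.** With the total fixed at 350, the smallest control group giving 80% power is 118 by the table's apparent method, 105 pooled with correction, 103 unpooled, 89 pooled and 88 by Wilcoxon. Even the most favourable figure is above 75.

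**Step 5: try other 15-point differences at 275/75.**

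| Control vs HCQ | Table's apparent method | Pooled |
|---|---|---|
| 25% vs 10% | 75.9% | 88.4% |
| 30% vs 15% | 69.7% | 81.6% |
| 35% vs 20% | 65.3% | 75.9% |
| 40% vs 25% | 62.2% | 71.3% |

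The shortfall depends on the base rate. At lower rates the pooled test passes 80%.

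**The case against.** The strongest reply is that section 7.5 contains no arithmetic error. Its 80% is conditional on two-thirds taking HCQ, it says the split is unknown, and at 230/120 the figure is right. That is correct: the fault is a conflict between sections, not a miscalculated row. But uncertainty about the split explains why several splits are shown. It does not explain why all of them break the caps while the one that fits is left out.

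A second reply is that the method is inferred. Section 7.5 offers 35% and 20% only as an example, and other formulas fit the three rows if the base rate is free. Unpooled without correction fits with an HCQ rate of 27% to 32%, and arcsine fits with 30% to 31%. For 35% vs 20% at 275/75 these give 70% and 74%. This point stands in part, so 65% should always be quoted with its formula and the 65% to 76% range. However, those alternatives give 84% to 85% for the plan's own example at 230/120, where 80% is stated. They also still put the detectable difference at 275/75 at about 0.18.

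Third, the missing row changes the detectable difference only from 0.17 to about 0.18. That is fair as regards the table. The worked example is hit harder, because it sits on the 230/120 row.

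Fourth, section 5.2.3 qualifies the cap with an approximation. The Protocol Summary and section 4.2.1 do not, and no ordinary reading stretches 75 to 118, or even to 88.

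**Conclusion.** The concern holds. As written, the plan's only power claim belongs to a split that its enrolment limits rule out. At 275/75 the 35% vs 20% example has about 65% power by the method that reproduces the table, and at most 76% by any method tried. The chance of missing that effect is thus about 35% (24% at best), against the 20% implied by the example. The detectable difference at 80% power is about 0.18 by the table's apparent method.

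That Group B is too small in every row follows from the text alone and needs no power formula. The size of the shortfall rests on the 35% and 20% rates and on the inferred formula. It also assumes that both caps are filled and that no controls are lost. Unreplaced moves from Group B to Group A could shrink the untreated group further. If, purely as an assumption, 60 controls remained against 275, the detectable difference would be about 0.20 by the same method.

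**What to change.** 1. State in section 7.5 the formula and the assumed rates behind the table.
2. Reconcile the Protocol Summary, section 4.2.1, section 5.2.3 and section 7.5 so that the caps and the tabulated splits agree.
3. If the caps stay, add a 275/75 row (about 0.18 by the table's apparent method) and restate the example for that split: about 65% power for 35% vs 20%, or the corresponding figure for whichever method is named.
4. If the caps move within 350 instead, match the example to the new split. At 260/90 it becomes the tabled 0.17, and 35% vs 20% has 72% by the table's apparent method. Keeping the 15-point example at 80% needs a Group B cap of about 118 to 120 by that method.
5. Label any row that allows for controls lost to switching as an assumption.

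Keeping the caps costs protocol wording, one recomputed row and a less favourable stated power, with no extra participants or procedures. Moving the caps keeps the total at 350 but changes the recruitment target for a self-selected group, so it is more than an edit.

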## 8 Source Documents

Source data is all information, original records of clinical findings, observations, or other activities in a clinical trial necessary for the reconstruction and evaluation of the trial. Source data are contained in source documents. Information from clinical parameters will be obtained from the Symptoms Questionnaire. A separate electronic dataset (using REDcap) will be constructed to capture the most important clinical information on the patients including the following: demographic information (gender, age, DOB, place of residence, ethnicity and race), presenting and daily symptoms and signs (including fever, cough, SOB, sputum production, anosmia, hyposmia, fatigue, sore throat, nasal congestion, diarrhea, headache, vital signs, pulmonary auscultatory findings)

Each person participating in this Study will be assigned a randomly generated study ID that will be linked to identifiers (MRN, DOB) in a linking table to be kept separate from the research data. Data and specimens will

be labelled with the study ID only. Only HRRC-approved members of the study team who have the appropriate training will have access to the data and identifiers. All data that we collect in this study will be entered into REDCap, a secure data-base, on a password-protected computer using a secure network. Any hard copy records/data will be kept in a locked file cabinet in the locked office of a designated member of the Study team. The specimens will be kept and stored in the Clinical and Translational Science Center at the UNM HSC and can only be accessed by the members of the study team. Investigators will transport the specimens to TriCore Reference Laboratories for lab analysis through standard transport hospital procedures. Once data collection is complete, data will be de-identified by destruction of the linking table.

Access to study records will be limited to IRB-approved members of the study team. The investigator will permit study-related monitoring, audits, and inspections by the IRB/EC, government regulatory bodies, and University compliance and quality assurance groups of all study related documents (e.g. source documents, regulatory documents, data collection instruments, study data etc.). The investigator will ensure the capability for inspections of applicable study-related facilities (e.g. pharmacy, diagnostic laboratory, etc.).

Participation as an investigator in this study implies acceptance of potential inspection by government regulatory authorities and applicable University compliance and quality assurance offices.

## **9 Ethics/Protection of Human Subjects**

### **9.1 Ethical Standard**

The investigator will ensure that this study is conducted in full conformity with Regulations for the Protection of Human Subjects of Research codified in 45 CFR Part 46, 21 CFR Part 50, 21 CFR Part 56, and/or the ICH E6.

### **9.2 Institutional Review Board (UNM HEALTH SYSTEMSC HRRC)**

The protocol, informed consent form(s), recruitment materials, and all participant materials will be submitted to the IRB for review and approval. Approval of both the protocol and the consent form must be obtained before any participant is enrolled. Any amendment to the protocol will require review and approval by the IRB before the changes are implemented to the study. All changes to the consent form will be IRB approved; a determination will be made regarding whether previously consented participants need to be re-consented.

### **9.3 Informed Consent**

An approved member of the study team will conduct the consent process with the participant in a private area of the hospital or by phone if needed. .

It may not be possible to have an in-person discussion of the study with participants. Investigators may need to conduct a phone consent via conference phone call because the investigator and participant may not be in the same location. Documenting written informed consent in these instances must involve a process as follows: the participant receives a copy of the informed consent document in advance of a telephone discussion. The investigator obtains consent over the telephone with the participant. A Legal Authorized Representative will not be required. Only English-speaking participants will be enrolled.

The informed consent form may be mailed, emailed or faxed to the participant. The consent discussion may then be conducted by phone, conference phone call or in person so that the participant can read the consent form during the discussion.

Investigators will explain the study to the potential participant by reading the informed consent document to the participant and provide all pertinent information (purpose, procedures, risks, benefits, alternatives to participation), and allowing the potential participant ample opportunity to ask questions. This can be done by phone, conference phone call or in person.

Investigators will ensure a thorough verbal discussion was conducted by phone, conference phone call or in person of the consent form. Investigators will allow the potential participant time to read the consent form and allow the participant sufficient time to consider whether or not to participate in the research.

Investigators will ensure the potential participant additional questions have been addressed.

Participants will be asked to explain the purpose of the study, procedures involved, and/or conditions for participation to confirm understanding.

If the participant agrees to participation, s/he signs the consent form and returns it to the investigator for signature and date. If informed consent took place via the phone or via conference phone call, the signed and dated consent form can be returned to investigators by mail, fax, or by scanning the consent form and returning it through a secure e-mail account by the participant. It is possible that multiple consent forms will be obtained for a single participant because the investigator obtaining consent and the participant were not in the same location but together via conference phone call. In this instance, each separate consent will be signed and dated by each individual appropriately. All dates on the multiple consent forms will be congruent for the day the consent took place. In these instances, a note-to-file will explain that separate consent forms exist for a single participant because all individuals could not be in the same room and that the consent took place over a conference phone call in an effort to decrease the contact and exposure to the novel coronavirus.

#### **9.4 Participant and Data Confidentiality**

Information about study subjects will be kept confidential and managed according to the requirements of the Health Insurance Portability and Accountability Act of 1996 (HIPAA). Those regulations require a signed subject authorization informing the subject of the following:

- What protected health information (PHI) will be collected from subjects in this study.
- Who will have access to that information and why.
- Who will use or disclose that information.
- The rights of a research subject to revoke their authorization for use of their PHI.

In the event that a subject revokes authorization to collect or use PHI, the investigator, by regulation, retains the ability to use all information collected prior to the revocation of subject authorization. For subjects that have revoked authorization to collect or use PHI, attempts should be made to obtain permission to collect at least vital status (i.e. that the subject is alive) at the end of their scheduled study period.

Participant confidentiality is strictly held in trust by the investigators and their staff. This confidentiality is extended to cover testing of biological samples and the clinical information relating to participants. Therefore, the study protocol, documentation, data, and all other information generated will be held in strict confidence. All study data will be stored in REDCap database. Participant electronic material are only labeled with study ID and the link to identifiable info is stored separately.

Representatives of the IRB may inspect all documents and records required to be maintained by the investigator, including but not limited to, medical records (office, clinic, or hospital) and pharmacy records for the participants in this study. The clinical study site will permit access to such records.

The study participant's contact information will be securely stored at the site for internal use during the study. At the end of the study, all records will continue to be kept in a secure location for as long a period as dictated by local IRB and Institutional regulations.

## **10 Data Handling and Record Keeping**

### **10.1 Data Collection and Management Responsibilities**

- Participants will be assigned a randomly generated study ID that will be linked to identifiers (MRN, DOB) in a linking table to be kept separate from the research data. Data and specimens will be labelled with the study ID only.
- Only HRRC-approved members of the study team who have the appropriate training will have access to the data and identifiers.
- Data will be entered into REDCap on a password-protected computer using a secure network.
- Any hard copy records/data will be kept in a locked file cabinet in the locked office of a designated member of the study team
- The specimens will be kept and stored in the Clinical and Translational Science Center at the UNM HSC and can only be accessed by the members of the study team. Then specimens will be transported to TriCore Laboratory and can only be accessed by laboratory personnel for the purpose specified in the protocol.
- Once data collection is complete, data will be de-identified by destruction of the linking table. Study records will be kept for 6 years past study closure.
- Biological samples collected for the study (e.g. blood) will not be stored in a repository, but will be destroyed after analysis and after completion of the study.

### **10.2 Protocol Deviations**

A protocol deviation is any noncompliance with the clinical trial protocol, GCP, or Manual of Procedures (MOP) requirements. The noncompliance may be either on the part of the participant, the investigator, or the study site staff. As a result of deviations, corrective actions are to be developed by the site and implemented promptly.

Protocol deviations must be reported to the local IRB per their guidelines. The site PI/study staff is responsible for knowing and adhering to their IRB requirements. Further details about the handling of protocol deviations will be included in the MOP.

### **10.3 Publication**

This study will adhere to the NIH Public Access Policy. UNM HEALTH SYSTEM will have the publication right of the papers as outcomes of this study.

## **11 Study Finances**

### **11.1 Costs to the Participant**

There will be no cost to the participant.

